For Aim #2: Primary outcome variables: Presence of abnormalities in the four laryngeal functions and two swallowing physiology measures.

Statistical analysis: For each outcome and independent variable, a univariate logistic regression model will be developed.

Overall Sample Size Determination: In a simulated data analysis, a sample size of 200 yielded an area under the curve (AUC) of .75 for the resultant tree algorithm. To be conservative, we will enroll a total of 225 patients.

Significance: For the 455,000 acute respiratory failure (ARF) survivors each year, aspiration is a devastating complication that can develop after the initiation of oral nutrition.^{1,2} Occurring in as many as 44% of ARF survivors, aspiration is associated with many deleterious consequences including pneumonia, percutaneous feeding tube placement, long term care facility admission, and increased hospital

mortality.³⁻⁶ The complications of aspiration must be weighed against the consequences of inappropriately delaying the resumption of oral feeding. Delayed resumption of oral nutrition is associated with prolonged enteral tube feeding, increased caregiver burden, patient dissatisfaction, and increased health-related costs.⁷⁻¹⁰ Improving the ability to easily and accurately diagnose aspiration in ARF survivors would both reduce the frequency and severity of aspiration and limit the problems associated with delaying oral nutrition. *This proposal will develop an effective non-invasive bedside diagnostic clinical prediction rule (CPR) to detect aspiration in ARF survivors.*

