survivors, abnormalities in laryngeal structure and swallowing physiology likely play a prominent role in the development of aspiration.²⁵ Specific abnormalities that may be responsible for aspiration include: laryngeal sensory defects and edema, vocal fold immobility and granuloma formation, delayed swallowing time, and reduced pharyngeal clearance.^{25;27-31} Building on our compelling data, the FEES examination will identify abnormalities associated with aspiration, and pave the way for the development for targeted therapies to prevent and treat aspiration.

[figure not shown]
Aim #1: To develop a BSE-based non-invasive clinical prediction rule (CPR) that will accurately and efficiently diagnose aspiration in ARF survivors.

Aim #2: To identify abnormalities in laryngeal structure and swallowing physiology that are associated with aspiration in ARF survivors.

[name] interest in dysphagia began with his 2000 *New England Journal of Medicine* article identifying the harmful effects of using blue dye to detect aspiration in ARF patients.³² Our multidisciplinary team established a strong collaboration with [name] and her exemplary research group at Boston University.^{26;33-49} [name] developed the FEES procedure and she is one of the pioneers of dysphagia-related research.^{50;51} These two productive research teams have contributed to the recent increased awareness of swallowing dysfunction and aspiration in ARF survivors.^{25;26;33;52} Collectively, we have

Figure 1: R21 Proposal Overview:

The outer circle represents our multidisciplinary infrastructure.

generated substantial preliminary data demonstrating both the need for better diagnostic CPRs and for studies that identify the mechanisms responsible for aspiration. Utilizing our established research infrastructures, we are ideally positioned to conduct and complete the proposed multidisciplinary research studies.

TRIAL DESCRIPTION

Background:

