Laryngeal sensation will be assessed by observing the laryngeal adductor reflex (LAR) or a patient response to a light touch/poke to the aerepiglottic folds bilaterally with the tip of the laryngoscope, and scored dichotomously.

Part 2: Standardized consistency testing: The SLP will then administer five standard consistencies in two trials of each consistency with different amounts.¹⁰⁶

Boluses will be administered from lowest to highest aspiration risk: 1) $\frac{1}{2}$ tsp, then 1 tsp ice chips, 2) 1 tsp of nectar thick liquids, then 3 tsp of nectar thick liquids, 3) a 2 ounce patient controlled administration of nectar thick liquids, 4) 1 tsp of pureed solids (applesauce), then 10 mls of pureed solids (applesauce), 5) 5 mls of thin liquids (water or milk), 15 mls of thin liquids (water or milk), and a 2 ounce patient controlled administration of thin liquids and 6) $\frac{1}{4}$ of a graham cracker.¹⁰⁷ The patient will be instructed to chew the graham cracker before swallowing. In order to limit the complexity and duration of our consistency testing, honey-thick liquids will be excluded from the protocol.

Table 3: PAS scoring system

Scale	Enters airway?	Relationship to vocal folds	Ejected from airway?	Effort made to eject?
1	No	--	--	--
2	Yes	Above	Yes	--
3	Yes	Above	No	--
4	Yes	Contacting	Yes	--
5	Yes	Contacting	No	--
6	Yes	Below	Yes	--
7	Yes	Below	No	Yes
8	Yes	Below	No	No

After the swallow, the laryngoscope will be advanced to closely view the patient's airway. The SLP will wait for 10 seconds following the completion of each individual trial before recording the results for that consistency. If necessary, patients will be allowed to drink water between consistency tests to clear any remaining residue from their upper airway.

The entire FEES will be video recorded. The SLP will score each of the trials using the PAS score (Table 3).

In addition for each of the trials of the consistencies, the SLP will record the following two physiological measures:

- 1) Swallowing onset time: The time from first bolus visualization until swallow onset.
- 2) Incomplete bolus clearance: leaving residue in the pharynx or laryngeal vestibule after a swallow.

Using the video recordings, the quantification of the swallowing onset time and incomplete bolus clearance will be determined by a single observer.

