include the next branches on the trees. By splitting the data up into ten sets and choosing one set each time, ten-fold cross-validation will estimate the misclassification rate for the tree. The chosen set will be sent through a tree developed from randomly choosing nine of the sets. The misclassification for this set will be calculated, and performed 10 times until each set has been sent through a tree. An average rate of misclassification is developed to determine how well the tree based on all the data will perform on new data.

Sample Size Calculation and Feasibility: Based on our 18 month data from the two medical centers, there were a total of 1087 patients who remained on mechanical ventilation for at least 48 hours and lived to be discharged to home or self-care. For recursive partitioning, there are no specific sample size calculations. However, in a simulated data analysis, a sample size of 200 yielded an area under the curve (AUC) of .75 for the resultant tree algorithm. To be conservative, we will enroll a total of 225 patients. Based on our estimated number of ARF survivors, we will need to obtain consent from only 20.6% of them to achieve our enrollment goal. This is a very conservative estimate for obtaining informed consent for research on swallowing function.

Additional Considerations: Our primary analysis will develop a CPR for the combined outcome of silent and non-silent aspiration. We will also develop a CPR for silent aspiration alone defined as a PAS score =8, and a CPR for non-silent aspiration alone defined as a PAS score of 6-7. For each of the five different consistencies, the accuracy of the BSE assessment for aspiration will also be compared to the presence of aspiration of the FEES examination (PAS ≥6). Sensitivity, specificity, positive and negative predicted values will be determined with 95% confidence intervals for each point estimate. Based on a sample size of 225 patients, the width of each 95% confidence interval point estimate will be 2-4%.

Statistical analysis for Aim #2: For each outcome and independent variable, a univariate logistic regression model will be developed. If the Wald test for an individual variable in the logistic regression model is significant at the p <0.10 level, the variable will be included in a multivariable logistic regression model. ROC curves will be constructed to determine how well the regression models correctly predict

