Epiglottic Retroflexion (during swallow)	 Complete  Reduced  Inconsistent  Absent  N/A
Granuloma Formation	 None  Mild  Moderate  Severe  N/A
Upper Airway Edema	 None  Mild  Moderate  Severe  N/A

Right Laryngeal Sensation touch on the aryepiglottic fold, if no sensation then repeat x1;	None	Mild	Moderate	Severe	N/A
Left Laryngeal Sensation touch on the aryepiglottic fold, if no sensation then repeat x1;	None	Mild	Moderate	Severe	N/A

Ice Chips (1/2 tsp)	PAS score <hr/>	Swallowing Onset Time <hr/>	Incomplete bolus clearance							
			Yes No							
Bolus given: YES NO	Not Determined	Not Done	Not Determined							
	If penetration (2-5): 
 
Before Swallow	During Swallow	
 
After Swallow		
 
 If aspiration (6-8): 
 
Before Swallow	During Swallow	
 
After Swallow		
 
	Before Swallow	During Swallow	After Swallow		Before Swallow	During Swallow	After Swallow		
Before Swallow	During Swallow									
After Swallow										
Before Swallow	During Swallow									
After Swallow										
Ice Chips (full tsp)	PAS score <hr/>	Swallowing Onset Time <hr/>	Incomplete bolus clearance							
			Yes No							
Bolus given: YES NO	Not Determined	Not Done	Not Done							
	If penetration (2-5): 
 
Before Swallow	During Swallow	
 
After Swallow		
 
 If aspiration (6-8): 
 
Before Swallow	During Swallow	
 
After Swallow		
 
	Before Swallow	During Swallow	After Swallow		Before Swallow	During Swallow	After Swallow		
Before Swallow	During Swallow									
After Swallow										
Before Swallow	During Swallow									
After Swallow										
Nectar Thick (5 ml) or 1 tsp	PAS score <hr/>	Swallowing Onset Time <hr/>	Incomplete bolus clearance							
			Yes No							
Bolus given: YES NO	Not Determined	Not Done	Not Done							

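### Aim 2 turns swallowing onset time, measured as a time, into normal/abnormal with no stated cut-off; a continuous analysis would keep substantially more information from data already collected

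*Combined protocol and SAP*

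**What the plan says.** The opening summary, under Aim #2, lists "Primary outcome variables: Presence of abnormalities in the four laryngeal functions and two swallowing physiology measures". The section on statistical analysis for Aim #2 adds: "For each outcome and independent variable, a univariate logistic regression model will be developed". Each measure is therefore analysed as yes/no. That section states 80% power at the 0.05 level for odds ratios of 2.5 to 3.0 with 178 to 271 observations. It gives no prevalences.

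The FEES section (Part 2) names the two physiology measures. The first reads "Swallowing onset time: The time from first bolus visualization until swallow onset". It is recorded for each trial, and one observer quantifies it from the recordings. The second, incomplete bolus clearance, is Yes/No on the form. The scoring sheet (Appendix, Part 4) has a blank for onset time on each of 11 bolus trials: two of ice chips, three of nectar-thick liquid, two of puree, three of thin liquid and one of solid.

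The four laryngeal measures are not listed under Aim 2. The Significance section suggests them: "laryngeal sensory defects and edema, vocal fold immobility and granuloma formation, delayed swallowing time, and reduced pharyngeal clearance". The scoring sheet grades cord mobility, granuloma, edema and sensation as "None Mild Moderate Severe". The FEES section, however, has sensation tested "with the tip of the laryngoscope, and scored dichotomously".

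**The concern.** Onset time is the one Aim 2 measure that is plainly quantitative, and it was collected at the cost of frame-level video reading. Reducing it to abnormal or not puts patients just over a line with those far beyond it. An association with aspiration that rises steadily with delay then becomes harder to detect.

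The definition is also incomplete. The protocol gives no cut-off, no unit and no rule for turning up to 11 times per patient into one value. If the cut-off is left open until the data are in, it can be chosen, knowingly or not, because it separates aspirators well. The nominal 5% error rate then no longer holds for that measure.

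**Working it through.** **1. The plan's own figure.** For a yes/no covariate with prevalence B and outcome probability p0 in the unexposed, the Hsieh formula is

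n = {z₁₋α/₂ √[P(1−P)/B] + z₁₋β √[p0(1−p0) + p1(1−p1)(1−B)/B]}² / [(p0−p1)²(1−B)], with P = (1−B)p0 + B·p1.

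The protocol gives neither p0 nor B, nor whether the test is two-sided (assumed here). With p0 = 0.12 and B = 0.38:
- odds ratio 3.0: p1 = 0.290, P = 0.185, n = 179
- odds ratio 2.5: p1 = 0.254, P = 0.171, n = 271

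Other pairs, such as p0 = 0.15 and B = 0.27 (179 and 270), fit as well. The range of 178 to 271 is attainable but cannot be confirmed. The continuous-covariate formula, n = (z₁₋α/₂ + z₁₋β)² / [P(1−P)(ln OR)²] with P the outcome rate, gives only 27 to 197 for outcome rates of 5 to 50%, and no rate tried gives 178 to 271. The stated range therefore looks like a yes/no calculation that already carries the cost of dichotomising.

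**2. Information kept by a cut.** If onset time is normal on some scale and a fraction q is called abnormal, the share kept is e = φ(c)²/[q(1−q)], where c is the cut in SD units. A test with 80% power uncut then has power Φ(√e × 2.802 − 1.960).

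| q abnormal | φ(c) | e | 80% becomes |
|---|---|---|---|
| 50% | 0.399 | 0.64 | 61% |
| 30% | 0.348 | 0.58 | 57% |
| 20% | 0.280 | 0.49 | 50% |
| 10% | 0.175 | 0.34 | 37% |

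**3. The same at the planned size.** Take N = 225 (sample size section) and 44% aspirating (Significance section), so 99 aspirators and 126 others. A continuous comparison has 80% power for a shift of 2.802 × √(1/126 + 1/99) = 0.376 SD. Cut where 50, 30, 20 or 10% of non-aspirators are abnormal, that shift is a yes/no odds ratio of 1.83, 1.84, 1.89 or 2.01, and power is 60, 59, 54 or 44%.

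**4. Simulated logistic models** (225 patients, 44% aspirating, Wald test, two-sided 0.05; effects assumed):

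| True relation | Continuous | Median cut | 75th percentile | 90th percentile |
|---|---|---|---|---|
| OR 1.5 per SD | 83% | 63% | 58% | 41% |
| Step at the 75th percentile, OR 2.5 | 56% | – | 80% | – |

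With no true association, taking the best of the three cuts rejects about 11% of the time. Repeat runs moved these figures by at most about three points.

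**5. At the plan's target effect.** With a yes/no odds ratio of 2.5 and 50, 30 or 20% of non-aspirators abnormal, power at 225 is 91, 91 and 86% cut, against 98 to 99% continuous. The size needed for 80% power is 161 to 189 cut, against 100 to 107 continuous. The cut analysis reaches 80% power at an odds ratio of 2.17 (30 to 50% abnormal), 2.33 (20%), 2.50 (15%) or 2.83 (10%).

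**6. The graded items.** For none versus any, under proportional odds, the information lost is 0 to 3% if 10 to 30% are abnormal, about 12% at 50%, and 32 to 48% at 70 to 80%. Equal-spaced scores were simulated for grade mixes of 15/35/30/20% and 40/30/20/10%. They move power from 45 to 83% and from 68 to 84% if risk rises by 1.5 per grade. If risk is flat above the lowest grade at odds ratio 2.5, they move it from 61 to 31% and from 91 to 74%.

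**The case against.** The strongest reply is that the plan is powered for what it does. Its odds ratios of 2.5 to 3.0 appear to be yes/no odds ratios, and at that size a cut onset time still has 86 to 91% power in the cases in step 5. This stands. The loss is relative to a better use of the same data and matters for smaller associations. A reader might infer that Aim 2 misses its stated 80% power. The documents do not show that, because the prevalences behind the figure are absent.

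A reader might also infer that all six measures lose much of their power. They do not. Bolus clearance is collected as Yes/No, and the protocol text scores sensation as two-level. For edema, granuloma and mobility the effect can go either way (step 6). Item 6 of the preliminary data calls upper airway abnormalities common but gives no prevalence, and its order of listing says nothing about frequency. Nor does the protocol define presence as any grade above the lowest. On the mobility rows, the lowest category could mean no impairment or no movement, so scoring it now could reverse the scale.

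It can also be said that a missing cut-off is not a data-chosen one. That is right: the 11% applies only if the cut is picked after looking, and fixing it beforehand removes that problem, though not the loss of information.

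Finally, a threshold relation is possible, and a cut placed at the true threshold would then win (80% against 56%). That needs the threshold to be known, and the protocol names none.

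**Conclusion.** The point holds for swallowing onset time. The plan dichotomises a measured time, gives no cut-off or rule for combining trials, and under a normal model would keep about 34 to 64% of the information, depending on where the cut falls. In the worked case that is about 83% power against 63, 58 or 41%. These sizes rest on an assumed distribution, an assumed odds ratio of 1.5 per SD, 44% aspirating and a two-sided test. The absence of a cut-off rests on the documents alone. For the graded laryngeal items the direction of benefit is unknown, so no loss is asserted. This is a worthwhile, inexpensive improvement and completes an outcome definition; it is not a failure of the trial's stated power.

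**What to change.** Before analysis, amend the Aim 2 analysis text as follows:

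- **Primary analysis of onset time.** Enter it as a continuous variable in a logistic model with aspiration as the response. Decide on a log transformation from its overall distribution, without reference to aspiration. The plan calls the abnormalities the outcomes, so this reverses the roles and should be stated openly. For a single yes/no pair the odds ratio is the same either way, but a continuous time cannot be the response in a logistic model.
- **Per-patient value.** State the unit, one summary across the bolus trials, and the handling of trials not given or not timed.
- **Secondary analysis.** Keep present/absent, with its cut-off fixed in advance. This covers a threshold relation.
- **Graded items.** State which grade counts as abnormal. Clarify what the lowest mobility category means, and reconcile sensation scoring between the FEES section and the form. Then add an ordered-grade analysis of edema, granuloma and mobility as a sensitivity analysis only.
- **Power statement.** Give the prevalences and sidedness behind 178 to 271.

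No new data or patients are needed. The cost is analysis-plan wording plus the decisions on the summary and the cut-off. The price in power is the threshold case: about 56% for the continuous term against 80% for a correctly placed cut.

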National Dysphagia Diet	Sens. (%)	Spec. (%)	PPV (%)	NPV (%)
Honey-thick liquids	29	56	33	50
Nectar-thick liquids	25	62	40	45
Thin liquids	38	75	60	55
Pureed solids	13	75	33	46
Regular solids	38	63	50	50

To develop a BSE-based non-invasive clinical prediction rule (CPR) that will accurately and efficiently diagnose aspiration in ARF survivors.

To identify abnormalities in laryngeal structure and swallowing physiology that are associated with aspiration in ARF survivors.

Primary Hypothesis: We hypothesize that the BSE assessment of swallowing certain consistencies will provide the most accurate diagnosis of aspiration.

1. Screening and recruitment:

Patients meeting enrollment criteria will be approached for informed consent no later than 72 hours after extubation. Surrogate consent may be used if patients are unable to provide their own informed consent due to lack of decisional capacity.

Inclusion Criteria: *Subjects will be eligible to participate in the study if they meet all of the following criteria:*

1. Admission to a University of Colorado Hospital ICU
2. Mechanical ventilation support through an endotracheal tube for greater than 48 hours

Exclusion Criteria:

1. Age < 18 years
2. Contraindication to enteral nutrition administration.
3. Pre-existing or acute primary central or peripheral neuromuscular disorder
4. Pre-existing history of dysphagia or aspiration.
5. Pre-existing head and neck cancer or surgery.
6. Presence of a tracheostomy.
7. Coagulopathy resulting in uncontrolled nasal or pharyngeal bleeding.
8. Unable to participate due to altered mental status
9. Extubated for greater than 72 hours.
10. Inability to obtain informed consent from patient or an appropriate surrogate.
11. Pregnancy
12. Imprisoned at the time of admission, anytime during the hospitalization, or anytime during the follow up period

If patients meet an exclusion criterion, they can be re-evaluated to determine if the exclusion criteria no longer exists; up to 72 hours after extubation. The presence of delirium is the one exclusion criterion that is

most likely to change over time and require repeated assessments.

There is no minimal amount of time that is required after extubation to be enrolled into the study (as long as the patient meets the inclusion criteria and does not currently meet any of the exclusion criteria).

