Part 3: Three Ounce Water Swallow Test (3-WST): During the standardized 3-WST, patients receive three ounces of water and are instructed to drink the entire amount, via cup or straw, completely and without interruption (the cup can be held to the patient's mouth by the SLP).^{74;76;109} The 3-WST will be scored based on the PAS scoring system.

The results of the different components of the FEES assessment will be made available to the treating team if requested.

The coordinator should make sure that the FEES CRF is completely filled out before the SLP who completed the test leaves the ICU. See Appendix for FEES evaluation form.

4. Outcome Assessments

All patients will be followed for the subsequent outcome assessments.

Date of ICU discharge

ICU length of stay

Date of hospital discharge

Hospital length of stay

Discharge location

Reintubation since enrollment

If yes, date of reintubation

Died during ICU stay

Died during hospital stay

Surgical feeding tube placed?

5. Statistical analysis for Aim #1: Recursive partitioning or Classification and Regress Tree (CART)

analysis creates a tree that asks a series of yes/no questions, taking the user down different branches depending on the answers. At the end of each branch will be an estimated probability of outcome.

Statistically, recursive partitioning is a non-parametric approach to regression, in this case logistic regression.

We will predict a class Y (aspiration vs. non-aspiration) based on the predictor variables, X₁...X_n which can be either categorical or continuous. The main characteristic of this method is that predictor variables are “split” and partitions are created so that observations with the same response variable are grouped together.

After the first split, further splits of variables will occur based on the groups which are made from the prior split separately. The goal is to group observations with the same response class minimizing

misclassification. Some of the benefits of using recursive partitioning are that the splits are data driven, predictor variables can be used multiple times, and interactions will be included without having to decide which interactions are important. An algorithm (or tree) is obtained that splits the predictor variables until each person has been classified as with aspiration or non-aspiration in a terminal node. Pruning of the tree will take place by determining a value of the change in misclassification rate which is deemed too small to

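### The primary hypothesis is comparative, but no planned analysis compares the consistencies with one another or with the rest of the bedside evaluation

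*Combined protocol and SAP*

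**What the plan says.** The hypothesis appears under Hypothesis and Specific Aims, again in the Significance text, and under Objectives, where it is labelled primary: "We hypothesize that the BSE assessment of swallowing certain consistencies will provide the most accurate diagnosis of aspiration". None of these places says which consistencies are meant, on which measure, or compared with what.

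Three parts of the statistical plan bear on it.

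- **Primary analysis** (Statistical analysis for Aim #1; Additional Considerations): "Our primary analysis will develop a CPR for the combined outcome of silent and non-silent aspiration". The method is recursive partitioning, pruned and assessed by ten-fold cross-validated misclassification. On how predictors enter, the plan says: "Some of the benefits of using recursive partitioning are that the splits are data driven".
- **Per-consistency analysis** (Additional Considerations): "For each of the five different consistencies, the accuracy of the BSE assessment for aspiration will also be compared to the presence of aspiration" on FEES, with aspiration defined as PAS ≥ 6. The output is: "Sensitivity, specificity, positive and negative predicted values will be determined with 95% confidence intervals for each point estimate". The precision claimed is: "Based on a sample size of 225 patients, the width of each 95% confidence interval point estimate will be 2-4" per cent.
- **Sample size**: "To be conservative, we will enroll a total of 225 patients", on the ground that in simulation "a sample size of 200 yielded an area under the curve (AUC) of .75 for the resultant tree algorithm". An alpha and a power are stated for Aim #2 only.

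Bedside Evaluation, Part 2 schedules one bolus sequence, in a fixed order, for all patients. It also lets the clinician stop when the next consistency seems unsafe, and the case report form has a yes/no field for whether each bolus was given.

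**The concern.** A claim that some consistencies are the most accurate needs a contrast: one consistency against another, or the consistency items against the history, the physical examination and the 3-ounce water test. The plan supplies neither. A tree may split on a consistency item without showing that it is more accurate than its rivals, and may pass over one because a correlated item was chosen first. Separate intervals describe each consistency against FEES but do not estimate the difference between two consistencies, and they ignore that the same patients contribute to both.

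At stake is the confirmatory value of the hypothesis that the protocol calls primary. As written, no planned result would count against it, and readers would be left to rank consistencies by eye from five sets of estimates. The claimed interval width adds to the risk, because it would make small differences look settled.

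**Working it through.** **1. The plan's own precision figure.** The number of aspirators is 0.44 × 225 = 99 (rate in the Significance text) to 0.50 × 225 ≈ 113 (pilot rate, Preliminary Data item 5). The 95% half-width is 1.96 × √(p(1−p)/n).

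- Sensitivity 38%, n = 99: 1.96 × √(0.38 × 0.62/99) = 9.6 points.
- Sensitivity 25%, n = 99: 8.5 points.
- Sensitivity 13%, n = 113: 6.2 points.

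The half-widths are thus about 6 to 10 points, and full widths about 12 to 19. The stated 2-4% does not reproduce. Using all 225 patients as denominator, half-widths at these sensitivities are still 4.4-6.3 points; only the bare standard error on 225 (2.2-3.2 points) falls inside 2-4%.

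**2. Inputs for a paired comparison.** Table 1 gives sensitivity 38% for thin and 25% for nectar-thick liquids, so d = 0.13. The within-patient correlation φ is not in the documents; I assume 0, 0.3 and 0.5. Alpha is taken as two-sided 0.05.

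- Both positive: p11 = p1·p2 + φ√(p1(1−p1)p2(1−p2)).
- Discordance: D = p1 + p2 − 2·p11. This is 0.440, 0.314 and 0.230 for φ = 0, 0.3 and 0.5.
- McNemar power = Φ[(d√n − 1.96√D)/√(D − d²)].
- Probability that separate 95% intervals do not overlap = Φ[(d − 1.96(se1 + se2))/√((D − d²)/n)].

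Lowest-power case (n = 99, φ = 0): (0.13 × 9.950 − 1.96 × 0.663)/0.650 = −0.01, so power is 0.50. Highest-power case (n = 113, φ = 0.5): (0.13 × 10.630 − 1.96 × 0.479)/0.461 = 0.96, so power is 0.83.

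Non-overlap, n = 99, φ = 0.5: (0.13 − 0.0956 − 0.0853)/0.0464 = −1.10, giving 0.14. For n = 113, φ = 0: (0.13 − 0.0895 − 0.0798)/0.0612 = −0.64, giving 0.26.

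| Aspirators | φ | McNemar power, α 0.05 | McNemar power, α 0.005 | Separate intervals do not overlap |
|---|---|---|---|---|
| 99 | 0 | 0.50 | 0.19 | 0.22 |
| 99 | 0.3 | 0.64 | 0.30 | 0.18 |
| 99 | 0.5 | 0.78 | 0.46 | 0.14 |
| 113 | 0 | 0.55 | 0.23 | 0.26 |
| 113 | 0.3 | 0.70 | 0.36 | 0.22 |
| 113 | 0.5 | 0.83 | 0.53 | 0.18 |

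The 0.005 column is Bonferroni for all pairs of five consistencies: 5 × 4/2 = 10 pairs, 0.05/10 = 0.005.

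**3. Precision of the difference.** The 95% half-width of the paired 13-point difference, 1.96√((D − d²)/n), runs from 8.5 points (n = 113, φ = 0.5) to 12.8 points (n = 99, φ = 0).

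**4. Boluses not given.** At φ = 0.3 and α 0.05, losing 10-30% of pairs (an assumed range) lowers power from 0.64-0.70 to 0.49-0.65. This counts lost pairs only, not any bias from selective stopping.

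**5. A larger pilot gap.** Thin against puree (38% against 13%) has power of at least 0.98 at α 0.05 and about 0.88 or more at 0.005. The trial can therefore separate consistencies that differ widely, but has modest power for smaller gaps.

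**The case against.** The best defence is that this is a development study. The Significance text puts the hypothesis next to the description of recursive partitioning, and Preliminary Data item 5 expects the gain to come from combining BSE components, since each consistency alone looks poor. Read that way, the hypothesis says that consistency items will drive the rule, and the tree speaks to that. This stands in part. A reader might infer that the plan can say nothing for or against its hypothesis; that goes too far, because the tree and the accuracy table would give descriptive evidence. What they lack is a contrast, a criterion for most accurate, and an error rate.

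Two other inferences are not supported. One is that consistencies will be ranked by whether intervals overlap: the plan states no such rule, so the overlap figures show only what informal reading would cost. The other is that every patient receives every consistency: that is the schedule, but the early-stopping provision and the form's bolus field allow gaps. Boluses run from lower to higher aspiration risk, so the gaps may fall selectively in the worst swallowers. This objection stands, and a complete-pairs McNemar test with no rule for gaps could be biased.

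It is also fair that an unadjusted single-pair power overstates what ten comparisons would deliver, as the 0.005 column shows.

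**Conclusion.** The concern holds in this form: the primary hypothesis is comparative, and the plan has no analysis that compares consistencies with one another or with the other BSE components. The tree gives exploratory evidence only, and the separate intervals do not supply the contrast.

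For the pilot thin-nectar gap, one paired test at 0.05 has about 50-83% power, against a 14-26% chance that separate intervals part. The range rests on 99-113 aspirators with complete pairs and on an assumed φ of 0-0.5. It falls to 19-53% under Bonferroni for all ten pairs. The pilot had 26 patients, so the gap itself is very uncertain. The case for change does not depend on these exact values: the paired data are already scheduled for collection. This is something the sponsor should fix, not a flaw that invalidates the study.

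**What to change.** In Additional Considerations (Aim #1):

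1. **Define the claim.** Name the metric as sensitivity and specificity against PAS ≥ 6 on any feeding. This matches the primary outcome and keeps the aspirator denominator common to all consistencies, which paired tests of sensitivity require.
2. **Add a paired comparison.** Begin with an overall test (Cochran's Q, or a GEE logistic model clustered by patient). Follow with paired differences, 95% confidence intervals and McNemar tests for a few prespecified contrasts, with multiplicity control.
3. **Add an analysis rule for boluses not given.** State how they are handled in the comparison, with a sensitivity analysis under another handling, because missingness may be selective.
4. **Compare with the rest of the BSE.** Report the difference in cross-validated AUC, on the same folds, between a tree built from Part 1 plus the 3-ounce water test and one that adds the consistency items. Label it incremental value; it does not by itself show that consistencies are the most accurate component.
5. **Correct the stated interval width** to agree with the denominators.

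If the sponsor does not want a confirmatory comparison, label the hypothesis exploratory.

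The cost is a little analysis work on data already planned, with no added procedures or patients. Power will remain modest for small differences, and the text should say so.
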